7.0 DISCONTINUATION OF STUDY INTERVENTION AND PARTICIPANT DISCONTINUATION/WITHDRAWAL

7.1 Discontinuation of Study Intervention

Participants may withdraw from the study at any time and for any reason without prejudice to their future medical care by the Investigator or at the study site. Every effort should be made to keep participants in the study.

If study treatment is discontinued, an end-of-treatment visit should occur 28 +/- 7 days after study treatment is discontinued or before a new treatment regimen begins. Participants who discontinue study drug should NOT be considered withdrawn from the study. Unless they withdraw consent or there is additional risk to the participant, participants who have discontinued study treatment should be encouraged to stay in the study and undergo as many scheduled visits as possible, with emphasis on the Week 48 (primary endpoint) and Week 96 (secondary endpoint) visits.

The reasons for study treatment discontinuation and/or withdrawal from the study (study discontinuation) will be recorded on the appropriate eCRF.

A participant may be withdrawn from the study for any of the following reasons:

- 1. The participant is non-compliant with the protocol;
- 2. The participant has a serious or intolerable adverse event(s) (AE[s]) that in the Investigator's opinion requires withdrawal from the study;
- 3. The participant has symptoms or an intercurrent illness not consistent with the protocol requirements or that justify withdrawal;
- 4. The participant is lost to follow-up;
- 5. Any medical condition that the Investigator or Sponsor determines may jeopardize the participants' safety if they remain in the study;
- 6. The participant withdraws consent, or the Investigator or Sponsor decides to discontinue the participant's participation in the study; or
- 7. Pregnancy.

The Investigator will also withdraw a participant if the Sponsor terminates the study. Upon occurrence of a serious or intolerable AE, the Investigator will confer with the Sponsor. If a participant is discontinued because of an AE, the event will be followed until it is resolved, or no additional improvement is expected by the Investigator (based on a follow-up period of not less than 3 months). Any participant may withdraw his or her consent at any time.

7.1.1 Treatment Interruption and/or Discontinuation due to Adverse Events or Concomitant Procedures

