7.1.1.4 Intercurrent Events

The following intercurrent events (ICEs) may impact the assessment of the primary efficacy endpoint:

- 1. Treatment misallocation at 1 or more study visits.
- 2. Use of prohibited medications in the study eye.
- 3. Development of sight-threatening complication(s) and initiation of open-label KSI-301 5 mg treatment, panretinal photocoagulation, or other treatment for DME, ASNV, and/or PDR.
- 4. Premature discontinuation from study treatment due to study eye adverse events or due to lack of efficacy.
- 5. Premature discontinuation from study treatment due to events unrelated to study treatment such as malignancies, systemic infections, trauma, or other systemic adverse events that are not treatment-related, including discontinuations due to COVID-19.

Intercurrent events will be classified by the Sponsor prior to treatment code unmasking to prevent potential bias. Intercurrent events and the time to intercurrent events will be tabulated and listed by treatment group. Strategies for addressing the potential impact of these intercurrent events are described below.

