7.3 Additional Secondary Efficacy Analyses

As specified in Section 4.0, the Primary Analysis will evaluate the efficacy of KSI-301 compared to sham from Day 1 up to Week 48.

Table 4 lists the additional secondary efficacy endpoints, efficacy variable derivations, reporting statistics and analysis methods for the Primary Analysis and until the end of study.

Binary secondary efficacy endpoints will utilize the Cochran-Mantel-Haenszel (CMH) method stratified by the randomization stratification factors (i.e. baseline DRSS level and HbA1c level).

Time to event endpoints will be analyzed using the Kaplan-Meier estimates. The number of observations censored will be provided for each treatment group. The 50th percentile of Kaplan-Meier estimates will be used to estimate the median time to first event in each treatment group. A 2-sided 95% CI will be provided for the estimates. A log-rank test stratified by the randomization stratification factors (i.e. baseline DRSS level and HbA1c level) will be performed to compare the survival distributions between the treatments. The hazard ratio and its 95% CI will be reported from a Cox regression model stratified by the same randomization stratification factors with treatment as the covariate. For patients not known to have had an event at the time of the analysis data cutoff, the time will be censored at the date of the last scheduled study visit at analysis data cutoff.

Continuous endpoints (e.g. mean change from baseline in BCVA) will utilize a Mixed Model for Repeated Measures (MMRM). The model assumes missing at random (MAR). The model will include the change from baseline value as the dependent variable; categorical covariates of treatment group, protocol scheduled visit, treatment × visit interaction, and the randomization stratification factors (i.e. baseline DRSS level and HbA1c level) as well as continuous covariate of baseline BCVA, as fixed effects; and then subject as a random effect. Within-subject correlations will be assumed to follow an unstructured covariance matrix. If the model assuming an unstructured covariance matrix does not converge, a heterogeneous compound symmetry structure or an AR(1) covariance structure will be fitted.

For all additional secondary efficacy endpoints, data after the occurrence of intercurrent event will be censored, and missing and non-gradable data will not be imputed. Only observed, gradable and non-censored data will be used for analysis.

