Additional Secondary Efficacy Endpoint	Variable Derivation [Source]	Summary Statistics [Analysis Set]	Method of Analysis		
Proportion of eyes developing PDR or ASNV from baseline through Week 48	Binary endpoint: patients developed PDR or ASNV (yes/no) [Sight-threatening Complication/EDC]				
Proportion of eyes developing vitreous hemorrhage or tractional retinal detachment, believed to be due to PDR, from baseline through Week 48	Binary endpoint: patients developed vitreous hemorrhage or tractional retinal detachment believed to be due to PDR (yes/no) [Sight-threatening Complication/EDC/Review of AEs]				
Proportion of eyes developing DME from baseline through Week 48	Binary endpoint: patients developed DME (yes/no) [Sight-threatening Complication/EDC]	Difference in proportions (%) and 95% CI at each time point [FAS], up to Week 48	CMH method adjusting for randomization stratification factors (similar to Section 7.1.2)		
Proportion of eyes with a ≥ 2 - step or a ≥ 3 -step worsening on DRSS from baseline at Week 48	Binary endpoints: patients with a ≥2-step worsening in DRSS (yes/no); patients with a ≥3-step worsening in DRSS (yes/no);				
Proportion of eyes who lose ≥ 5 , ≥ 10 , or ≥ 15 letters in BCVA from baseline by visit over time	Binary endpoints: patients had a BCVA loss \geq 5 (yes/no); patients had a BCVA loss \geq 10 (yes/no); patients had a BCVA loss \geq 15 (yes/no). [Visual Acuity Score/EDC]				
Time to first development of PDR, ASNV, or DME through Week 48	Time to event endpoint: Time from first treatment to development of PDR, ASNV, or DME (in months) [Sight-threatening Complication/EDC]				

Table 4: Additional Secondary Efficacy Endpoints and Analysis Methods

KS301P106 SAP Version 0.1 KSI-301 – Kodiak Sciences Inc.

Additional Secondary Efficacy Endpoint	Variable Derivation [Source]	Summary Statistics [Analysis Set]	Method of Analysis			
Time to first development of PDR or ASNV through Week 48Time to event endpoint: Time from first treatment to development of PDR or ASNV (in months) [Sight-threatening Complication/EDC]						
Time to first development of vitreous hemorrhage or tractional retinal detachment, believed to be due to PDR through Week 48	to first development of us hemorrhage or onal retinal detachment, red to be due to PDR gh Week 48		Kaplan-Meier and Cox regression model stratified by randomization stratification factors (Section 7.3)			

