of AEs] Time to first development of DME through Week 48 Time from first treatment to development of DME (in months) [Sight-threatening Complication/EDC]						
Mean change in SD-OCT central subfield thickness (CST) from baseline by visit over time	Continuous Endpoint: Change from baseline to each time point	LS Mean difference in change from baseline to each time point and 95% CI [FAS], up to Week 48 [FAS], up to end of study	MMRM (Section 7.3) adjusting for baseline CST, with time, treatment, and time*treatment interaction and randomization stratification as factors Unstructured covariance matrix			
Mean change in BCVA from baseline by visit over time	Continuous Endpoint: Change from baseline to each time point [Visual Acuity Score/EDC]	LS Mean difference in change from baseline to each time point and 95% CI [FAS], up to Week 48 [FAS], up to end of study	MMRM (Section 7.3) adjusting for baseline BCVA, with time, treatment, and time*treatment interaction and randomization stratification as factors Unstructured covariance matrix			

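### BCVA recorded after a treatment stop or a switch to open-label KSI-301 is left out of the BCVA endpoints, and SAP Section 8 has no BCVA summary, so whether vision loss after those events persists to Week 48 is not summarised

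*SAP*

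**What the plan says.** SAP 7.3 covers all additional secondary efficacy endpoints. It states that "data after the occurrence of intercurrent event will be censored, and missing and non-gradable data will not be imputed", and then: "Only observed, gradable and non-censored data will be used for analysis". SAP Table 4 places under this rule the proportions losing ≥5, ≥10 or ≥15 "letters in BCVA from baseline by visit over time", and also "Mean change in BCVA from baseline by visit over time". The mean change is fitted by MMRM under a missing-at-random assumption.

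Section 7.3 has no list of intercurrent events of its own. The full list is in SAP 7.1.1.4. One item is "Premature discontinuation from study treatment due to study eye adverse events or due to lack of efficacy". Another is development of a sight-threatening complication with the start of open-label KSI-301 or other treatment.

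The protocol expects these participants to keep being measured. Protocol 7.1 says: "Participants who discontinue study drug should NOT be considered withdrawn from the study". It adds that "participants who have discontinued study treatment should be encouraged to stay in the study and undergo as many scheduled visits as possible". Both schedules of activities (Protocol 1.3.1 and 1.3.2) place BCVA at every visit through Week 96.

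Protocol 9.4.3 handles BCVA differently. It fills missing post-baseline efficacy values by LOCF, and the only values it censors are DRSS scores after a sight-threatening complication. It also lists the proportion of eyes with prolonged vision loss, an endpoint that appears in neither SAP Table 1 nor SAP Table 4.

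**The concern.** Letter loss is where a reader looks for visual harm from an intravitreal drug. If an eye stops treatment because of a study-eye adverse event and its vision stays poor, the visits that would show this are collected and then left out. The same applies to vision after a switch for DME, PDR or ASNV.

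Removal can also depend on the outcome itself. One of the two DME definitions in Protocol Table 3 requires a decrease of at least 5 letters from Day 1. An eye that meets it switches, and its later BCVA is censored, so the ≥5-letter endpoint can lose an eye because that eye lost 5 letters. For the same reason, missing at random is a doubtful assumption for the mean BCVA model, and no planned between-arm BCVA analysis uses all observed values.

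**Working it through.** **What remains visible.** The endpoints are by visit, so BCVA before the event counts at its own visit. What drops out is every later visit, including Week 48. The SAP does not say whether a discontinuation is dated at the last dose or at the decision to stop. If it is the last dose, the visit at which the loss was found may also be removed.

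**Illustration for the KSI-301 arm.** The documents give no rate of vision loss or of stopping for a study-eye adverse event, so there is no plan figure to reproduce. The only input from the documents is about 120 participants per arm (Protocol 9.2). Assumptions:
- k KSI-301 eyes stop for a study-eye adverse event and have a lasting ≥15-letter loss that is measured at Week 48.
- b other eyes in each arm have such a loss.
- There are no other missing data.
- Censored eyes leave the denominator, following the 7.3 restriction to observed data.

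Planned rate = b/(120 − k). All-observed rate = (b + k)/120.

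| b | k | planned, KSI-301 | all observed, KSI-301 | sham |
|---|---|---|---|---|
| 0 | 1 | 0/119 = 0.0% | 1/120 = 0.8% | 0.0% |
| 0 | 3 | 0/117 = 0.0% | 3/120 = 2.5% | 0.0% |
| 0 | 6 | 0/114 = 0.0% | 6/120 = 5.0% | 0.0% |
| 2 | 1 | 2/119 = 1.68% | 3/120 = 2.50% | 2/120 = 1.67% |
| 2 | 3 | 2/117 = 1.71% | 5/120 = 4.17% | 1.67% |
| 2 | 6 | 2/114 = 1.75% | 8/120 = 6.67% | 1.67% |

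With b = 2, the difference from sham is 0.01 to 0.09 points as planned and 0.8 to 5.0 points with all observed BCVA. If the full FAS denominator of SAP 7.1.2 were used instead, the planned rate would be b/120 and the k eyes would still not show.

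**Illustration in the other direction.** Assume that 30 of 120 sham eyes switch, that 40% of these have lost ≥5 letters, and that 10% of the other 90 have. All observed: (30 × 0.4 + 90 × 0.1)/120 = 21/120 = 17.5%. Planned: 9/90 = 10%. Here the rule hides loss in the sham arm.

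**What SAP Section 8 would catch.**
- It covers exposure, adverse events, pregnancies, IOP, laboratory values and vital signs. It has no summary of BCVA values.
- The AESI table counts study-eye adverse events with a ≥30-letter drop, severe inflammation, or surgery to prevent permanent loss of sight (Protocol 8.3.6). The drop is measured from the last assessment, not from baseline, and the table combines study-eye, fellow-eye and non-ocular events.
- The treatment-emergent window closes 28 days after the last dose, or earlier at a switch. For an eye last dosed at Week 20 it ends at Week 20 + 4 = Week 24, and the next scheduled visit is Week 32. Protocol 7.1 also asks for an end-of-treatment visit about 28 days after discontinuation, which may or may not fall inside the window.
- Adverse events after treatment discontinuation are listed, with no summary of their own. For switched eyes, study-eye events are summarised, but BCVA is not.
- The BCVA summaries in SAP 7.4 are optional and descriptive, and cover only switched eyes.

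A loss of 5 to 29 letters from baseline after a stop therefore reaches no summary of BCVA values. It shows only in listings, or if it is reported as an adverse event.

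**The case against.** A reader might infer three stronger things, and the documents support none of them.

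- That lasting vision loss caused by KSI-301 cannot appear in these endpoints. It can: loss before the event counts at its visit. Protocol Table 5 calls for interruption, with possible resumption, for active intraocular inflammation and for treatment-related loss of ≥30 letters. The listed event is premature discontinuation, so an eye that is only interrupted stays in the analysis unless another event occurs.
- That letter loss is the only tabulated measure of visual harm. Section 8.2 also tabulates AESIs, ocular events leading to discontinuation, ocular events by severity and intraocular inflammation. The AESI line is not worded as treatment-emergent, so the 28-day limit may not apply to it. SAP 5.1 puts collected data in listings.
- That the rule favours the drug. It applies to both arms, and the two illustrations point in opposite directions. PDR, ASNV and the second DME definition (CST ≥350 microns) require no letter loss, so the assumed 40% among switched sham eyes has no support in the documents.

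Three further points carry weight. These are efficacy endpoints outside the hierarchical family, and censoring matches the hypothetical strategy used for the primary endpoint. Applying the 7.1.1.4 list to 7.3 is a reading, and SAP 7.2.1 shows that the list can vary by endpoint. SAP Section 10 gives the SAP's definitions precedence over the protocol's. So the censored analysis is a legitimate choice, and whether an all-observed version should replace it is an estimand trade-off. None of this supplies the missing summary of BCVA after the event. Nor does Section 10 name the change in BCVA handling or the loss of the prolonged vision loss endpoint, although SAP 1.0 says that changes will be described and explained there.

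**Conclusion.** The point stands as a gap in reporting. BCVA after a treatment stop for a study-eye adverse event, or after a switch, is scheduled but then left out of the letter-loss and mean-change endpoints. Persistence of loss to Week 48 in those eyes is not summarised, and Section 8 fills the gap only in part. Under the stated assumptions, 1 to 6 affected KSI-301 eyes of 120 would move the all-observed ≥15-letter rate by 0.8 to 5.0 points, while the planned rate would move by less than 0.1 point. These counts are assumptions, and the net direction across both arms is unknown. The conclusion rests on reading the 7.1.1.4 list into 7.3 and on participants continuing to attend, which the protocol encourages but cannot guarantee. It should be corrected. It does not affect the primary endpoint or the key secondary tests.

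**What to change.** 1. Add to SAP Section 8 a table by visit to Week 48, on the Safety Analysis Set, of ≥5-, ≥10-, ≥15- and ≥30-letter loss from baseline. Use all observed BCVA regardless of treatment stop or switch, with a footnote that values after a switch include open-label KSI-301.
2. Add the same all-observed version on the FAS as a supplementary analysis beside the censored analysis in 7.3.
3. State in 7.3 which intercurrent events apply, and state the date that defines a discontinuation event.
4. Restore the protocol's prolonged vision loss endpoint, or explain its removal in SAP Section 10. Record there the change from LOCF to censoring for BCVA.

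The cost is SAP wording and a few extra tables from data already scheduled for collection. The drawback is that sham values after a switch reflect open-label drug, so the all-observed table describes what happened to vision in each randomized or treated group and does not isolate the effect of masked treatment.

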Participants who develop any of the sight-threatening complications of DR in the Study Eye that are described in Table 3 will be treated with open-label KSI-301 5 mg, irrespective of the treatment group that they were originally randomized into (KSI-301 5 mg or sham). The original treatment group randomization will remain masked throughout the study.

At the visit that a sight-threatening complication of DR (DME, PDR and/or ASNV) is diagnosed (i.e., the "Dx Visit"), treatment with open-label KSI-301 5 mg will be initiated. Starting at the Dx Visit, participants will no longer follow the study visits and assessments outlined in Section 1.3.1 (SoA-A), nor receive further masked treatments. Instead, they will follow the study visits and assessments outlined in Section 1.3.2 (SoA-B), which is specific to the participants who develop DME, PDR, and/or ASNV.

As shown in Figure 2, treatment of DME, PDR, and/or ASNV will consist of the following:

 Two doses of KSI-301 5 mg, given four weeks apart (+/- 7 days), followed by KSI-301 5 mg once every 12 weeks (Q12W; +/-14 days). Thus, the first dose shall occur during the study visit in which DME, PDR, and/or ASNV was diagnosed, and the second dose shall occur 4 weeks (+/- 7 days) later. Thereafter, subsequent doses shall occur Q12W (+/-14 days).

More frequent visits and more frequent treatments with KSI-301 5 mg and/or panretinal photocoagulation (PRP) are at the discretion of the Investigator if the sight-threatening complication(s) as described in Table 3 are still present. Treatment with KSI-301 5 mg may not be given more often than monthly $(28 \pm 7 \text{ days})$.

End of Study Considerations

For participants who develop any of the sight-threatening complications described in Table 3, the following shall be considered:

- Participants shall not receive any treatment with KSI-301 5 mg after Week 92 (i.e., 92 weeks after the day of randomization (Day 1)).
- Weeks 96 and 100 (relative to the day of randomization (Day 1)) include final safety assessments that are mandatory and shall also be conducted according to the SoA-B (Section 1.3.2).

Figure 2:Protocol KS301P106: Dosing Regimen by Week for All Participants
Who Develop Sight-threatening Complication(s) in the Study Eye

	Q4W (±	7 days)	C	12W (± 14 day	SE	SA	
Week	Dx Visit	Dx Visit + 4 Weeks	Dx Visit + 16 Weeks	Dx Visit + 28 Weeks		96	100 ^b
KSI-301 5 mg ^a							
KSI-301 5 mg via intravitreal injection							treatment Visit

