2.0 STUDY OBJECTIVES AND ENDPOINTS

Table 1 lists the primary, key secondary and additional secondary study objectives, along with their corresponding endpoints.

Table 1: Objectives and Endpoints

Table 1: Objectives and Endpoints Objectives	Corresponding Endpoints
	Corresponding Endpoints
Primary To demonstrate that KSI-301 5 mg is superior to sham treatment, with respect to proportion of eyes improving ≥2 steps on Diabetic Retinopathy Severity Scale (DRSS) from baseline at Week 48.	• The proportion of eyes improving ≥2 steps on DRSS from baseline at Week 48.
Key Secondary	
To demonstrate that KSI-301 5 mg is superior to sham treatment, with respect to proportion of eyes with vision-threatening complications of diabetes, and proportion of eyes improving \geq 3 steps on Diabetic Retinopathy Severity Scale (DRSS).	 Proportion of eyes developing any of the following from baseline through Week 48: PDR or ASNV; Vitreous hemorrhage or tractional retinal detachment believed to be due to PDR; or DME.
	• Proportion of eyes improving ≥3 steps on DRSS from baseline at Week 48.
	• Proportion of eyes developing PDR through Week 48.
Additional Secondary	
To evaluate the efficacy of KSI-301 5 mg compared to sham treatment.	• Proportion of eyes developing PDR or ASNV from baseline through Week 48.
	• Proportion of eyes developing vitreous hemorrhage or tractional retinal detachment, believed to be due to PDR, from baseline through Week 48.
	• Proportion of eyes developing DME from baseline through Week 48.
	• Proportion of eyes with a ≥2-step worsening from baseline on DRSS from baseline at Week 48.
	• Proportion of eyes with a ≥3-step worsening from baseline on DRSS from baseline at Week 48.
	• Time to first development of PDR, ASNV, or DME through Week 48.
	• Time to first development of PDR or ASNV through Week 48.
	• Time to first development of vitreous hemorrhage or tractional retinal detachment, believed to be due to PDR through Week 48.
	• Time to first development of DME through Week 48.
	• Mean change in SD-OCT central subfield thickness (CST) from baseline by visit over time.
	• Mean change in BCVA from baseline by visit over time.
	• Proportion of eyes who lose ≥ 5 , ≥ 10 , or ≥ 15 letters in BCVA from baseline by visit over time.

KS301P106 SAP Version 1.0 KSI-301 – Kodiak Sciences Inc.

Objectives	Corresponding Endpoints
To evaluate the safety and tolerability of KSI-301	Incidence of ocular and systemic adverse events up to Week 48.

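### SAP 7.3 appears to censor an eye at its first treated complication, so the two vitreous hemorrhage/tractional detachment endpoints through Week 48 would miss later events

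*SAP*

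**What the plan says.** Two additional secondary endpoints concern the same outcome. SAP Table 4 has "Proportion of eyes developing vitreous hemorrhage or tractional retinal detachment, believed to be due to PDR, from baseline through Week 48", derived as "patients developed vitreous hemorrhage or tractional retinal detachment believed to be due to PDR (yes/no"), and SAP Section 2.0 also lists "Time to first development of vitreous hemorrhage or tractional retinal detachment, believed to be due to PDR through Week 48".

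SAP 7.3 sets one rule for the whole group: "For all additional secondary efficacy endpoints, data after the occurrence of intercurrent event will be censored". It adds: "Only observed, gradable and non-censored data will be used for analysis". It does not say which list of intercurrent events it means.

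The only general list is in SAP 7.1.1.4, introduced for the primary endpoint. Its third event is "Development of sight-threatening complication(s) and initiation of open-label KSI-301 5 mg treatment, panretinal photocoagulation, or other treatment" for DME, ASNV and/or PDR. Under Protocol 4.1.3.1, at the visit where a complication is diagnosed, "treatment with open-label KSI-301 5 mg will be initiated".

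Three other passages bear on the reading:

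- SAP 7.2.1 gives a separate four-item list for the key secondary composite, which includes this same hemorrhage/detachment outcome. Event 3 is not on it. SAP 7.2.3 adopts that list; 7.3 neither adopts nor cites it.
- SAP 7.3 also says, for time-to-event endpoints, that patients without a known event are censored at their last scheduled visit at data cutoff. Intercurrent events are not mentioned there.
- Protocol 9.4.1 and 9.4.3 name only DRSS scores for censoring after a complication. SAP Section 10.0 gives the SAP's intercurrent-event strategies precedence.

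**The concern.** Event 3 lies on the pathway to the outcome. Take an eye found with new vessels at Week 20, treated that day, that bleeds or detaches at Week 32. If event 3 censors, that eye contributes no event to either endpoint. Treated DME or ASNV would censor the eye in the same way.

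The endpoints would then record hemorrhage or detachment present at or before the first treated complication, although they are labelled as running through Week 48. The censoring is also informative: it is triggered by the condition that leads to the outcome, and its frequency will differ by arm if KSI-301 prevents complications. These are among the most severe outcomes in the plan, so a published Week 48 rate that leaves out later events would be misleading.

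**Working it through.** **Text.** With the 7.1.1.4 list, the chain is: complication diagnosed → open-label treatment at the same visit → event 3 → all later data out of the Table 4 analyses. With the 7.2.1 list, the second and third links do not censor and the problem disappears. The text of 7.3 does not settle which applies.

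**Follow-up discarded** = 48 − week of diagnosis. For a first diagnosis at Week 8, 20, 32, 44 or 48 this is 40, 28, 16, 4 or 0 weeks. SAP SoA-B continues eye examinations, fundus photographs and AE review after diagnosis, so the data are collected.

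**Size.** The documents give no rate for this outcome, so there is no plan figure to reproduce and the following inputs are all assumed:

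- p = share of an arm with PDR by Week 48 (5–25%), exponential onset, detected and treated at the next SoA-A visit w (Weeks 8, 20, 32, 44, 48);
- s = share already showing hemorrhage or detachment at that visit (5–20%);
- r = annual probability of a first event after that visit (10–30%).

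Counted = p × s.
Lost = (1 − s) × Σ d(w) × [1 − (1 − r)^((48 − w)/52)], where d(w) is the share of the arm first detected at w.
True = counted + lost.

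Example with p = 25%, s = 10%, r = 20%:

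| w | d(w), % | later event, % | product, % |
|---|---|---|---|
| 8 | 4.68 | 15.77 | 0.738 |
| 20 | 6.62 | 11.32 | 0.749 |
| 32 | 6.16 | 6.64 | 0.409 |
| 44 | 5.73 | 1.70 | 0.098 |
| 48 | 1.82 | 0 | 0 |

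The products sum to 1.99%. Lost = 0.90 × 1.99% = 1.79%; counted = 2.50%; true = 4.29%. Missed share = 1.79/4.29 = 42%. Per 120 eyes, 3.0 events are counted and about 2.15 are lost.

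Over the assumed ranges the missed share runs from 13% (p = 5%, s = 20%, r = 10%) to 70% (p = 25%, s = 5%, r = 30%). The events lost per 120 eyes run from about 0.2 to 3.5.

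**Between arms**, with p = 25% against 5%, s = 10% and r = 20% in both:

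| | higher-PDR arm | lower-PDR arm | ratio | difference |
|---|---|---|---|---|
| counted | 2.50% | 0.50% | 5.0 | 2.0 points |
| true | 4.29% | 0.84% | 5.1 | 3.45 points |

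The missed share is 42% and 41%.

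**Denominator.** The proportions above keep a censored eye in the denominator as a no. SAP 7.3 does not say whether to do that or leave the eye out. Leaving out the eyes censored without an event changes the example to 2.5/(100 − 22.5) = 3.2%, still below 4.29%. With p = 25%, s = 20%, r = 10% it gives 5.0/(100 − 20) = 6.25% against a true 5.78%, which is too high. So the event count is understated either way, but the direction of the error in the proportion depends on an unstated choice. Kaplan-Meier censoring at diagnosis gives about 2.8% at Week 48 in the example, also below 4.29%.

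**The case against.** The strongest reply is that 7.3 never says event 3 applies. The list in 7.1.1.4 is introduced for the primary endpoint. Where the SAP treats complications as outcomes, in 7.2.1, it drops event 3, and the Table 4 row for the hemorrhage/detachment proportion adds a review of AEs to its sources, which hints at a search beyond the diagnosis-visit form. The time-to-event version also has its own cutoff-based censoring sentence. This stands as far as it goes: the rule is ambiguous, not settled. But the 7.2.1 list is confined to its own endpoint, and the rule in 7.3 covers every additional secondary endpoint without exception, so a programmer following the text could well apply event 3.

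A reader might infer that the endpoints are nearly empty because hemorrhage only follows PDR. Protocol Table 3 makes vitreous hemorrhage itself a PDR criterion, so hemorrhage as the presenting sign counts. Tractional detachment is not listed there and is more exposed.

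A reader might also infer that unequal loss between arms manufactures a benefit for KSI-301. With the same presentation share and later event rate in both arms, the calculation does not show that: the ratio barely changes and the absolute difference shrinks.

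The stakes are limited. The numbers of events are small, and SAP 8.2 still summarizes study-eye adverse events after the switch, though it does not say by randomized arm. Counting events after both arms can receive open-label KSI-301 also answers a different question from the censored analysis, which is why both should be shown.

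**Conclusion.** The point holds as a conflict to be resolved. If the 7.1.1.4 list governs 7.3, both endpoints capture only events present at or before the first treated complication, and they are informatively censored. That disagrees with 7.2.1 for the same outcome and, in the time-to-event version, with the other censoring sentence in 7.3.

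The size, 13–70% of events missed or roughly 0.2–3.5 per 120 eyes, rests wholly on assumed rates. It covers censoring by PDR only, not by DME or ASNV. The direction for event counts does not depend on those rates. The understated rates and absolute difference assume that censored eyes stay in the denominator.

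The documents do not support reading this as a threat to the main conclusions. The two endpoints lie outside the hierarchical family in SAP 7.2, and the primary and key secondary results are unaffected.

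**What to change.** In SAP 7.3, and in a footnote to Table 4, state that for the two vitreous hemorrhage/tractional detachment endpoints (proportion and time to first event) the 7.2.1 list of intercurrent events applies, so event 3 does not censor. Count the first such event through Week 48 by randomized arm. Leave the other intercurrent events as they are.

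Reconcile the two censoring sentences in 7.3 for the time-to-event version. For the proportion, say whether an eye censored without an event is a no or is left out. Report the version censored at event 3 as supportive, described as events at or before the first treated complication.

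The cost is a few sentences and one extra supportive analysis. No new data are needed and patient management does not change. The downside is that open-label KSI-301 in both arms may dilute the difference between them, which should be said when the result is reported.
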